Randomization will be done through an independent study coordinator or research fellow other than the one who is assessing the outcomes. Patients will be randomly assigned to one of the two groups as 1:1 ratio.

The nurse who is responsible for operating the radiofrequency generator will be the only one informed about the randomization results through the unblinded study coordinator. The physician and the patient will both be blinded.

Intravenous access will be inserted for all patients and mild sedation with midazolam will be given according to the patient needs.

With the C-arm guidance a 20-gauge radiofrequency needles with 10mm active tips will be used to ablate 3-4 lumbar facet medial branches.

At each level, needles will be adjusted to optimize sensory and motor stimulation. For each nerve lesion, correct placement is confirmed using electrostimulation at 50Hz, with concordant sensation achieved at 0.5V or less. Before denervation, multifidus stimulation and the absence of leg muscles contractions is verified with electrostimulation at 2Hz.

The radiofrequency lesions will then be carried out at 80°C (group 1) or

90°C (group 2) for 90 seconds twice to produce the desired lesions of the medial branches.

• Data Collection:

Study data for follow-up visits will be collected by one of 3 ways. The follow-up visit questionnaires can be filled in-person, sent out to patients by mail or completed over the phone, whichever is more convenient for the patient.

Collected data will then be inputted and managed using REDCap (Research Electronic Data Capture) tools hosted at Cleveland Clinic. REDCap is a secure, web-based application designed to support data capture for research studies, providing:

1) An intuitive interface for validated data entry.

2) Audit trails for tracking data manipulation and export procedures.

3) Automated export procedures for seamless data downloads to common statistical packages.

4) Procedures for importing data from external sources.

• Patient Demographics:

- Age
- Sex
- Smoking
- BMI
- History of back surgeries.

Page ${\bf 9}$ of ${\bf 16}$

Protocol Version 3 Revision Date: 10/15/2019

- Diabetes mellitus.
- Response to diagnostic blocks

• Patient Baseline data:

- Preoperative and baseline pain score will be collected using Visual Analog Scale (VAS)
- Pain Questionnaires:
 - Pain Disability Index (PDI).
 - McGill Pain Questionnaire.
 - Beck Inventory (BI)
- Oral pain medications in morphine sulfate equivalent mg/day.

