• Technique related data:

- The temperature of the probe used (80°C or 90°C)
- Duration of application of the RF probe is 90 seconds twice using 10mm active tip probe.
- Sensory stimulation 0.5mAmp
- Needle size 20G
- The number of ablated nerves.
- Side/Laterality.

• Outcomes Data:

Outcomes will be measured at baseline and 1, 3, 6 and 12 months follow-up visits post-procedure.

Primary outcomes:

Overall pain relief (i.e. percent of improvement) at each visit mentioned above.

Secondary outcomes:

- Postoperative Pain Scores in the subsequent visits using VAS at each visit mentioned above.
- Pain Questionnaires:
 - Pain Disability Index (PDI).
 - McGill Pain Questionnaire.
 - Beck Inventory (BI)
- Number of repeats of procedure in the first year after index procedure.

• Consumption of oral opioids in mg oral morphine equivalents recorded at the baseline before the procedure and then in the follow-ups post-procedure (1, 3, 6 and 12months).

- This table summarizes the morphine equivalent doses for the most commonly used morphine derivatives (7).

Drug Name	Oral dose equivalent to 30mg oral morphine sulfate	IV dose equivalent to 30mg oral morphine sulfate			
Morphine sulfate	30 mg (1:1 ratio)	10 mg (1:3)			
Hydromorphone	7.5 mg (1:4 ratio)	1.5 mg (1:20)			
Meperidine	300 mg(10:1 ratio)	100 mg (3.33:1)			
Methadone	12mg(1:2.5 ratio)	10 mg (1:3)			
Oxycodone	15 mg(1:2 ratio)	N/A			
Hydrocodone	30 mg(1:1 ratio)	N/A			
Codeine	200 mg(6.66:1 ratio)	120 mg (4:1)			

- The following formula will be used for Fentanyl transdermal patch:

- \circ 25 µg/h is equivalent to 87.5 mg morphine/24h
- \circ 50 µg/h is equivalent to 175 mg morphine/24h
- \circ 75 µg/h is equivalent to 262.5 mg morphine/24h
- \circ 100 µg/h is equivalent to 350 mg morphine/24h

• Adverse Events:

- Persistent paresthesia (yes/no)
- Nerve injury (yes/no)
- Infection (yes/no)
- Bleeding (yes/no)

• Data Analysis:

Standard descriptive statistics will be used to compare the randomized groups on baseline variables. Any obviously imbalanced co-variables (say, with a standardized difference greater than 0.20 in absolute value) will be adjusted for in both primary and secondary analyses. Our primary analysis will be intent-to-treat.

Primary Hypothesis:

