Graphically displayed over follow-up times (1, 3, 6 and 12 months) using boxplots containing the median, quartiles and outliers. At each follow-up time point (1,3, 6 and 12 months) we will assess whether 80°C and 90°C RFA temperatures differ with respect to the percentage of pain relief using the Wilcoxon rank-sum test. The significance criterion will be 0.05/4=0.0125 at each time, using a Bonferroni correction to control the type I error at 0.05 for the primary hypothesis. In addition to the P-value, the estimated median percentage of pain relief for each group and difference in medians with confidence intervals will be reported. The estimated probability of pain relief at 90°C being better than at 80°C with confidence interval will be reported, since the Wilcoxon rank sum test has a null hypothesis that this probability is 0.50. All the confidence intervals will be estimated based on bootstrapped standard error with 10,000 bootstrap replications (8).

Interim analyses:

Interim analyses will be conducted for efficacy and futility at each 25% of the maximum enrollment (see Sample Size Considerations) using a group sequential design and gamma spending function (using gamma = -4 for efficacy and -2 for futility). P-value boundaries for efficacy (futility in parentheses) will be P \leq 0.0016 (P>0.957), P \leq 0.0048 (P>0.719), P \leq 0.0147 (P>0.239), and P \leq 0.0440 (P>0.0040) at looks 1 through 4, respectively.

• Secondary hypotheses: We will compare randomized groups on the following variables:

VAS pain scores/Pain Disability Index (PDI)/McGill Pain questionnaire scores/Beck Inventory (BI) scores.

While the detailed description below focuses on the VAS pain score outcome for brevity, the analysis approach will be the same for Pain Disability Index (PDI), McGill Pain questionnaire scores, and Beck Inventory (BI) scores.

Graphical analysis will be undertaken to describe the degree of pain reduction observed in patients undergoing each treatment. The association between RFA temperature and pain reduction will be performed using a mixed effects model adjusting for time interval and also for baseline pain score to increase precision. We will assess the group-time interaction and assess treatment effects at each time if interaction P <0.15. The mixed model will account for potential intra-subject correlation of repeated VAS pain measurements within a patient using a spatial

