correlation structure. A model-based Wald test for regression model coefficients will be used to evaluate whether or not RFA temperature affects mean pain reduction.

Opioid Consumption:

As preliminary retrospective study showed, postoperative opioid consumption is largely binary in nature for this patient's population, as over 60% of our patients did not take any opioids. Thus, postoperative opioid consumption within a year of the first RFA will be analyzed as a binary outcome, i.e., any versus none (however, dosage information among the subset of patients taking any opioids will be described using medians and quartiles for each group). Multivariable logistic regression will be used to estimate the adjusted relative risk for postoperative opioid use comparing patients undergoing RFA at 90°C to patients undergoing RFA at 80°C. A logistic model-based Wald test for regression coefficients will be used to test the hypothesis of the effect of temperature on the postoperative opioids use (i.e., whether or not the relative risk is different from a value of 1.0).

Number of repeat of RFA procedures

Need for repeated RFA procedure over one year period will be analyzed as a count variable using a proportional odds logistic regression model. If the number of repeats greater than 1 is very rare, we will use a binary outcome of any RFA procedure comparing two groups of patients.

Complications:

Incidence of each individual complication will be reported for each group, with confidence intervals. Possible adverse events (persistent paresthesia, nerve injury, bleeding and infection) will be summarized into a single composite binary outcome, i.e., any versus none. The risk of experiencing one or more adverse events will be compared between RFA at 90°C and RFA at 80°C groups using logistic regression.

Type I error will be controlled at 5% for the secondary outcomes using the Bonferroni correction for simultaneous hypotheses. SAS 9.3 software (SAS Institute, Cary, NC) and R statistical software version 2.7.2 (The R Foundation for Statistical Computing, Vienna, Austria) will be used for all analyses and graphics.

Sample size considerations:

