Sample size estimation is based on the frequency distribution estimated across four categories of pain relief used in our preliminary retrospective study. Thus, for these calculations 38%, 9%, 37%, and 16% of patients undergoing RFA at 80°C are assumed to develop no improvement (=0%), minimal improvement (<25%), moderate improvement (25-75%), and marked improvement (>75%) in symptoms, respectively. We further assumed that the data was uniformly distributed across each category through simulation, and performed power calculations on the simulated data using categories of percent pain relief of 0, 1-10, 11-20, 21-30, \dots , 91 – 100. In order to have 90% power at the 0.0125 significance level at each time point (0.05/4 = 0.0125 at each time point) to detect a clinically significant shift in improvement of absolute 15% between RFA at 90°C and RFA at 80°C, a maximum of N=216 total patients would be required. Below we list the proportion of patients in each percent pain relief category as assumed for the sample size calculations described above. Although a 20% increase is in general what would be considered a clinically important improvement in pain relief, we plan for 15% since there may be a nontrivial fraction of patients who experience no relief in either group. Adjusting for 3 interim analyses and a final analysis would require a maximum of N=237. With the above parameters, there will be a cumulative 8%, 37%, 75%, and 100% chance of crossing a boundary at the 1st through 4th analyses if the alternative hypothesis is true as stated above.

Group	0	1-10	11-20	21-30	31-40	41-50	51-60	61-70	71-80	81-90	91-100
Control	.38	.041	.035	.06	.07	.067	.069	.087	.062	.057	.072
Experimental	0	0	.399	.041	.03	.083	.068	.064	.077	.078	.16

We plan to re-estimate sample size after obtaining at least 1 and 3 month continuous pain relief outcome for the first 60 patients, using the observed shape of the distribution and the variability of the outcome, but still based on an absolute 15 percent upward shift from the 80 degrees group. Type I error will be controlled using the methods in Kieser 2000 (9).

We will provide results to the Data and Safety Committee on efficacy and safety assessments, including conditional power analyses, but the committee will have final say on whether the study would progress to the next interim analysis or be stopped.

References

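### The primary analysis adjusts only for covariates imbalanced by chance and names no adjusted test; a prespecified rank ANCOVA on baseline data already collected would be clearer and at least as efficient

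*Combined protocol and SAP*

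**What the plan says.** The Data Analysis section compares the arms descriptively at baseline. For variables that look imbalanced it then states: "say, with a standardized difference greater than 0.20 in absolute value) will be adjusted for in both primary and secondary analyses". The cutoff is offered as an example, not as a fixed value.

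Under Primary Hypothesis, one test is named. The arms are compared "with respect to the percentage of pain relief using the Wilcoxon rank-sum test" at 1, 3, 6 and 12 months, and "The significance criterion will be 0.05/4=0.0125 at each time". The accompanying estimates (medians, their difference, and the probability that 90°C does better) carry no covariates either.

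Under Secondary hypotheses, the VAS model adjusts for time and "also for baseline pain score to increase precision", and the same approach is extended to PDI, McGill and BI scores. The Patient Baseline data list shows that baseline VAS is collected, and so is opioid dose: "Oral pain medications in morphine sulfate equivalent mg/day".

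**The concern.** Two things look wrong.

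- **The adjusted primary test is undefined.** A Wilcoxon rank-sum test takes no covariates. If the 0.20 rule fires, the plan promises an adjusted primary analysis but names no method for it. It also does not say whether the adjusted or the unadjusted result governs.
- **Chance imbalance is a poor way to choose covariates.** Precision comes from adjusting for variables that predict the outcome, whether or not they are imbalanced. Under correct randomization, imbalance says nothing about prognosis, so the rule will mostly adjust for variables that do not matter and miss those that do.

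The plan accepts fixed adjustment for precision in its secondary models, but its primary outcome gets none. At stake are efficiency and a clear statement of which test decides the trial.

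**Working it through.** **Inputs.** Per-visit significance level 0.0125, taken as two-sided because the plan tests for a difference (Primary Hypothesis). The 11-category outcome table, 90% power, and N=216 fixed or 237 with interim looks (Sample size considerations). 1:1 allocation (Study Protocol). Twelve baseline variables: seven under Patient Demographics and five under Patient Baseline data.

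**Step 1: reproduce the plan's sample size.** Both rows of the table sum to 1, and P(90°C better) plus half the tie probability is 0.6477. Noether's formula for the Wilcoxon test gives

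N = (2.498 + 1.282)² / [3 × (0.6477 − 0.5)²] ≈ 218.4,

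or 213.8 with the tie factor 0.979. Both agree with the plan's figure ("a maximum of N=216 total patients would be required") to within about 1%. The sample size therefore rests on an unadjusted Wilcoxon.

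**Step 2: how often the rule fires.** Under randomization the standardized difference is approximately normal with mean 0 and variance 2/n, where n is the number per arm.

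- N=237 (n=118.5): 2 × [1 − Φ(0.20/√(2/118.5))] = 0.1237
- N=216 (n=108): 0.1416
- At least one of 12 at N=237, independent: 1 − (1 − 0.1237)¹² = 0.795. With pairwise correlation 0.3 or 0.5 (simulated): 0.724 or 0.617
- Only the five Patient Baseline data items: 1 − (1 − 0.1237)⁵ = 0.483. With correlation 0.3 or 0.5: 0.448 or 0.393

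If the rule were applied at each planned look (N about 59, 119, 178, 237), the chance per variable would be 44%, 28%, 18% and 12%, so the covariate set could change from look to look.

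**Step 3: power.** Outcomes were simulated from the plan's table, at one visit with a single analysis. Two of the 12 covariates were prognostic and shared a latent R²: one normal (standing for baseline VAS) and one binary, split 40/60 (standing for any opioid use). The split is an assumption based on the statement that "over 60% of our patients did not take any opioids", which describes postoperative use. The plan names no adjusted method, so the rule was run as a linear model on ranks with the selected covariates, or as the Wilcoxon if none was selected. The rank ANCOVA was Quade's. There were 10,000 trials per scenario, with a Monte Carlo standard error of about √(0.93 × 0.07/10,000) = 0.26 points.

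| Per arm | Test | R²=0 | 0.05 | 0.1 | 0.2 | 0.3 |
|---|---|---|---|---|---|---|
| 118 | Wilcoxon | 93.4% | 93.3% | 93.3% | 93.2% | 93.4% |
| 118 | 0.20 rule | 92.8% | 92.8% | 93.1% | 93.8% | 94.5% |
| 118 | Rank ANCOVA | 93.1% | 94.1% | 95.0% | 96.7% | 98.3% |
| 108 | Wilcoxon | 90.5% | 90.7% | 90.7% | 90.8% | 91.0% |
| 108 | 0.20 rule | 89.7% | 90.3% | 90.6% | 91.6% | 92.5% |
| 108 | Rank ANCOVA | 90.3% | 91.6% | 92.7% | 95.0% | 97.0% |

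The rule selected a given prognostic covariate in 12.7 to 13.3% of trials at 118 per arm.

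**Step 4: type I error.** With 20,000 null trials per scenario and nominal 0.0125, rejection was 0.012 to 0.014 for the Wilcoxon, 0.009 to 0.014 for the rule and 0.012 to 0.015 for the rank ANCOVA. The rule becomes conservative as R² rises.

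**Step 5: how often the choice matters.** At the planned effect and 118 per arm, the Wilcoxon and the rule gave different verdicts in 1.7% of trials at R²=0, rising to 3.0% at R²=0.3. At R²=0.2 with correlated covariates the figure was 3.7 to 4.0%.

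**The case against.** The strongest reply is that the gain depends wholly on an R² the documents do not give. Percent improvement is already relative to baseline, so R² may be small. Between R² of 0 and 0.1 the rank ANCOVA changes power at 118 per arm by only −0.3 to +1.7 points, on a test that already exceeds its target. This stands as a limit on the size of the benefit.

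The parallel with the secondary models is also imperfect, because they adjust each score for its own baseline value and percent relief has none. That is fair: the plan is not contradicting itself here. The rule can also be read as a safeguard for balance and not as a device for precision. Even so, a safeguard needs a defined method, and the plan gives none.

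The remedy has a cost too. The Wilcoxon P-value matches the reported probability that 90°C does better, while a rank ANCOVA P-value would sit beside unadjusted estimates. In simulation (8,000 trials, 118 per arm) the two tests disagreed in 2.1%, 3.2%, 4.2% and 5.0% of trials at R² of 0.05, 0.1, 0.2 and 0.3. Much of that is the power gain itself, so the cost is small.

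Finally, amendments run from 2014 to 2019, so interim looks may already have been made with the Wilcoxon. This is the most practical objection, and it decides which form of the fix applies.

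**Conclusion.** The point holds as an inexpensive improvement, not a fatal flaw. The text gap is certain: imbalance-triggered adjustment of the primary analysis is promised, and no adjusted primary method exists. The rule is likely to fire, in roughly 62 to 80% of trials if all 12 variables are screened and 39 to 48% if only five are. It changes power by only about −0.5 to +1.2 points at 118 per arm, against −0.3 to +4.9 points for the rank ANCOVA. These figures rest on the plan's outcome table, an assumed R² of 0 to 0.3, an assumed opioid split, and one visit analysed once. Type I error is not inflated by a fixed rank method, and the unadjusted Wilcoxon meets the 90% target on its own.

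**What to change.** Remove the 0.20 trigger from the primary analysis and name one primary test per visit: a rank ANCOVA of percent pain relief on baseline VAS and baseline opioid use (any versus none, the form the plan uses for postoperative opioids).

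- Rank percent relief over both arms, regress the ranks on ranked baseline VAS and the opioid indicator, and compare the residuals between arms.
- Replace a missing baseline value by the pooled mean, so that the intent-to-treat set is unchanged.
- Report the unadjusted Wilcoxon, the medians and the probability that 90°C does better alongside.
- Apply the plan's significance criterion to that one test. How 0.0125 per visit fits with the interim boundaries (final P≤0.0440) must be reconciled separately.

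If interim looks have already used the Wilcoxon, which the documents do not say, changing the primary test mid-trial is more than a wording change. In that case keep the Wilcoxon as the sole primary test, still remove the trigger from the primary analysis, and prespecify the rank ANCOVA as supportive.

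The cost is a protocol amendment and no new data, since both covariates are recorded before the procedure. If neither is prognostic, the price is about 0.3 points of power (93.1% against 93.4% at 118 per arm), which is close to simulation error.

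### The printed interim efficacy boundaries are built on two-sided alpha 0.05 for a single test, while the plan allots 0.0125 to each of four time points

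*Combined protocol and SAP*

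**What the plan says.** Under Data Analysis, Primary Hypothesis, percent pain relief is tested by the Wilcoxon rank-sum test at 1, 3, 6 and 12 months, and "The significance criterion will be 0.05/4=0.0125 at each time, using a Bonferroni correction to control the type I error at 0.05". The Outcomes Data section makes relief at every visit primary and singles none out.

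Under Interim analyses, "Interim analyses will be conducted for efficacy and futility at each 25% of the maximum enrollment", with a "gamma spending function (using gamma = -4 for efficacy and -2 for futility"). The section continues: "P-value boundaries for efficacy (futility in parentheses) will be" 0.0016 (0.957), 0.0048 (0.719), 0.0147 (0.239) and 0.0440 (0.0040) at looks 1 to 4. It does not give the alpha behind these values or the time point they apply to, and it does not say that P-values are adjusted before comparison.

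Under Sample size considerations, the fixed-design size of 216 is for "90% power at the 0.0125 significance level at each time point (0.05/4 = 0.0125 at each time point"). It rises to 237 for the interim looks, and under the alternative "there will be a cumulative 8%, 37%, 75%, and 100% chance of crossing a boundary" at the four analyses.

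**The concern.** The two sections give different rules for the same test. A final P of 0.03 at one time point succeeds under 0.0440 and fails under 0.0125. A P of 0.014 at look 3 would stop the trial for efficacy while missing the plan's own per-time-point level.

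The plan makes its Bonferroni correction by lowering the criterion to 0.0125, so the natural reading is that unadjusted P-values are compared with the printed boundaries. On that reading the 5% control claimed for the primary hypothesis is not assured. This is the primary decision rule and the early-stopping rule, so the choice between readings should not be left until data have been seen.

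**Working it through.** **Inputs.** Four tests at 0.0125 each; looks at 25, 50, 75 and 100%; gamma -4 (efficacy) and -2 (futility); 90% power, so beta = 0.10; fixed N 216, maximum 237. The two-sided form is inferred from the wording that the temperatures differ, and the match below supports it. Information is assumed equal to the enrollment fraction.

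**Step 1: where the boundaries come from.** The gamma (Hwang-Shih-DeCani) function spends α(1 − e^(4t))/(1 − e^4) by information fraction t when gamma = -4. With α = 0.05:

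- t = 0.25: 0.05 × 1.718/53.598 = 0.0016
- t = 0.50: 0.05 × 6.389/53.598 = 0.0060
- t = 0.75: 0.05 × 19.086/53.598 = 0.0178
- t = 1: 0.05

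Recursive numerical integration turns this spending into nominal boundaries. Futility uses a symmetric non-binding two-sided design.

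| Quantity | Printed | Two-sided α 0.05 | Two-sided α 0.0125 |
|---|---|---|---|
| Efficacy P, looks 1–4 | 0.0016, 0.0048, 0.0147, 0.0440 | 0.0016, 0.0048, 0.0147, 0.0440 | 0.0004, 0.0012, 0.0035, 0.0105 |
| Futility P, looks 1–3 | 0.957, 0.719, 0.239 | 0.957, 0.719, 0.239 | 0.930, 0.484, 0.096 |
| Maximum N from 216 | 237 | 216 × 1.0966 = 236.9 | 216 × 1.084 = 234.2, so 235 |
| Cumulative crossing, alternative | 8/37/75/100% | 8/37/75/100% | 7/35/75/100% |

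One-sided 0.05 gives 0.0016, 0.0049, 0.0151, 0.0452 and does not match. The sequential layer was therefore built at two-sided 0.05. The printed look 4 futility value of 0.0040 does not fit: the same design gives 0.0440, equal to the efficacy boundary, so it looks like a digit error.

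**Step 2: the alpha behind 216.** The tabulated distributions give P(90°C better), with ties counted half, of 0.648. Noether's formula for 1:1 allocation is N = (z_α/2 + z_β)²/[3(P − 0.5)²].

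- Two-sided 0.0125: (2.498 + 1.282)²/(3 × 0.1477²) ≈ 218 (213.8 with tie correction), close to the printed 216.
- Two-sided 0.05: about 158 to 161.

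Sample size and stopping rule thus rest on different alphas.

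**Step 3: type I error at one time point.** With the printed boundaries on unadjusted P-values and futility non-binding, cumulative error is 0.16%, 0.59% and 1.78% at looks 1 to 3. It ends at 4.99% with final criterion 0.0440, or 2.39% with final 0.0125. With binding futility, look 3 stands at 1.76% and the totals are 4.6% and 2.34%. The allotment is 1.25%. No correlation between time points enters here.

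**Step 4: family-wise error.** If the four time points were independent, the totals are 1 − (1 − 0.0499)^4 = 18.5% and 1 − (1 − 0.0239)^4 = 9.2%. Simulation of 1,000,000 trials per correlation, with equal correlation, equal information and non-binding futility, gives:

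| Assumed correlation | 0 | 0.3 | 0.5 | 0.7 | 0.9 |
|---|---|---|---|---|---|
| Final 0.0440 | 18.5% | 17.4% | 15.7% | 13.1% | 9.4% |
| Final 0.0125 | 9.2% | 8.8% | 8.0% | 6.8% | 4.8% |

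If interim looks are run at one time point only and all four use 0.0125 at the end, the bound is 2.39 + 3 × 1.25 = 6.1%.

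**Step 5: operating characteristics at N = 237.** The drift is (2.498 + 1.282) × √(237/216) = 3.96.

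- Boundaries recomputed at 0.0125: power about 90.4%, crossing 7/36/75/100%.
- Printed boundaries on unadjusted P-values: crossing about 13/51/86/100%, power about 96% (final 0.0440) or 93% (final 0.0125).

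**The case against.** The strongest defence is that the boundaries were meant for P-values already multiplied by four. The raw efficacy boundaries would then be 0.0004, 0.0012, 0.0037 and 0.0110. They spend 1.30% per time point, and family-wise error is 5.1% (independent) to 2.7% (correlation 0.9). The stated crossing chances also sit much closer to this reading than to the unadjusted one. But the documents nowhere say it, and the printed futility values cannot sensibly be used on multiplied P-values. It stands as an acceptable clarification if it is written down, with futility restated.

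A second defence treats the boundaries as a guide for the committee, which has the final say on continuing, with significance also requiring P ≤ 0.0125. That still spends about 2.2% per time point. The committee's discretion does make the non-binding futility figures the relevant ones.

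A third point is that looks are set by enrollment while outcomes arrive at 1 to 12 months, so equal information at all four time points is unrealistic. This is fair, and the family-wise figures are illustrations. It does not help the plan: with information of 10/35/60% or 5/25/50% at looks 1 to 3, the look 3 spend rises to 1.86% or 1.91%.

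Finally, high correlation between visits reduces the family-wise error. Only the final-0.0125 reading at a correlation of 0.9 falls below 5%, and Bonferroni was chosen so that no correlation need be assumed.

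**Conclusion.** The concern holds and must be fixed. The printed efficacy boundaries belong to a single test at two-sided 0.05 and conflict with the 0.0125 on which the testing rule and the sample size rest. That conclusion needs no assumption about correlation, since all four efficacy values reproduce at 0.05 and none at 0.0125.

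The size of the error depends on a reading the plan does not settle. On unadjusted P-values a time point's 1.25% is already exceeded at look 3, so declaring 0.0125 the final criterion does not rescue the rule. The family-wise ranges rest on assumed correlations and equal information. Power, maximum N and crossing chances barely move once the boundaries are repaired; they do move if the printed boundaries are used on unadjusted P-values.

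**What to change.** Recompute the boundaries with the same gamma functions at two-sided alpha 0.0125 per time point. At 25/50/75/100% information:

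- efficacy: P ≤ 0.0004, 0.0012, 0.0035, 0.0105
- futility: P > 0.930, 0.484, 0.096, 0.0105 (this also replaces the printed final futility value of 0.0040)

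State that these apply to unadjusted P-values, which time points are tested at each look, and that the look 4 boundary replaces the bare 0.0125. Where a time point has a different information fraction at a look, including after the planned sample-size re-estimation, recompute its boundary from the same spending function. For example, assumed information of 10/35/60/100% gives efficacy boundaries of 0.0001, 0.0006, 0.0018 and 0.0113. At equal information the family-wise error is then 4.9% (independent) to 2.6% (correlation 0.9).

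A near-equivalent for efficacy is to state that the printed boundaries apply to P-values multiplied by four, again with futility restated.

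The cost is wording and four boundary pairs. No extra patients are needed: the recomputed maximum is 235, so 237 can stay, subject to the planned re-estimation, with crossing chances restated as about 7/36/75/100%. The downside is that early stopping for efficacy becomes harder than with the printed boundaries.

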In a retrospective study done at our department, 100 patients (50.3%) received RFA at 80°C and 99 patients (49.8%) received RFA at 90°C. there were no clear cut advantage of either

temperature. However, the preliminary analysis did not control for potentially confounding baseline demographics and disease related characteristics. Thirty eight (38%), 9 (9%), 37 (37%) and 16 (16%) patients undergoing RFA at 80°C reported no improvement, minimal improvement (<25%), moderate improvement (25-75%), and marked improvement (>75%) in symptoms respectively. Among patients undergoing RFA at 90°C, these numbers were 19 (19%), 1 (1%), 44 (45%) and 34 (35%), respectively. The proportional odds logistic regression model for relief did not indicate a significant difference in relief scores between the two groups (likelihood ratio test p=0.033, using an adjusted significant difference criterion at 0.025). Due to the factors discussed and the inherent limitations of the retrospective studies, we plan to prospectively study the issue in a double-blinded randomized fashion.

Study Population:

• Patient Population:

Subjects with chronic low back pain (LBP) of lumbar facet joints origin fulfill the other below inclusion criteria and do not meet any of the exclusion criteria will be recruited from Cleveland Clinic Pain management outpatient clinic.

• Inclusion Criteria:

- a. Age >18 years-old.
- b. Subjects who are able to give informed consent and to understand and comply with study requirements.
- c. Predominantly axial low back pain \geq 3 months in duration with no radicular pain below the knee that failed to conservative therapy.
- d. Subjects who have chronic back pain attributed to lumbar facet joints arthropathy based on clinical evaluation (paraspinal tenderness and/or facet loading test in the absence of signs and symptoms suggestive of focal neurological deficits).
- e. No history of previous back surgery at the intended treatment levels.
- f. Adequate response to the diagnostic block(s), 1 or more, at the same levels of the intended block (defined as \geq 70% pain relief).
- g. Patients who will undergo RFA of 3-4 lumbar facet medial branches on one side only.

• Exclusion Criteria:

- a. Subjects who decline to provide written consent or follow-up.
- b. Subjects who have a history of adverse reactions to local anesthetic.
- c. Subjects who are pregnant.

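### Is the difference in medians too imprecise, and too dependent on the share of patients with no relief, to serve as the primary effect size in points?

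*Combined protocol and SAP*

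**What the plan says.** In the combined protocol and SAP, the Primary Hypothesis text under Data Analysis plans boxplots at each visit and a Wilcoxon rank-sum test at 0.0125 per visit. Two estimates accompany the P-value. The first is in points of relief: "the estimated median percentage of pain relief for each group and difference in medians with confidence intervals will be reported". The second is on the scale of the test: "The estimated probability of pain relief at 90°C being better than at 80°C with confidence interval will be reported". The plan gives its reason for the second, namely that the Wilcoxon null hypothesis sets this probability to 0.50. On method it says "All the confidence intervals will be estimated based on bootstrapped standard error with 10,000 bootstrap replications". No confidence level is stated.

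Sample size considerations assumes that 38%, 9%, 37% and 16% of 80°C patients have no, minimal, moderate and marked improvement, and it looks for an absolute 15-point shift. It remarks that "there may be a nontrivial fraction of patients who experience no relief in either group". In the department's retrospective series (Summary of Literature), 38% had no improvement at 80°C; for 90°C, "these numbers were 19 (19%), 1 (1%), 44 (45%) and 34 (35%), respectively".

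**The concern.** With 38% of 80°C patients at exactly zero and only 9% between 0 and 25, the 80°C median (about 29) lies close to a sparse band and a point mass. A median there is estimated poorly, so a trial could report a significant P-value beside a median-difference interval that includes 0.

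If 90°C works by reducing the number of non-responders, the median difference could also rise or fall between visits as the no-relief share changes, although the treatment does the same thing each time. For opioid use the plan does adapt to a pile-up at zero, choosing a binary outcome "as over 60% of our patients did not take any opioids"; for the primary outcome it does not. At stake would be how readers judge the size of the effect in points.

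**Working it through.** **1. The plan's own figure.** From the 11-category table in Sample size considerations, P(90°C better), with ties counted half, is 0.6477. Noether's formula for equal arms, two-sided 0.0125 and 90% power gives N = (2.498 + 1.282)² / [3 × (0.6477 − 0.5)²] ≈ 218. A tie-corrected version gives 214, and simulated power at N = 216 is 90.6%. The stated 216 is reproduced. The difference in medians plays no part in it.

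**2. Width.** Take 118 per arm (237/2), with values uniform within the table's categories.
- Mean difference: true value 13.8. With SDs of 33.9 and 31.6, SE = √[(33.9² + 31.6²)/118] ≈ 4.3, so the 95% half-width is 1.96 × 4.3 ≈ 8.4.
- Median difference: true value about 16. Simulating the planned bootstrap-SE interval (600 trials, 1,000 resamples each) gives a 95% half-width of 22.4 and coverage of 94.5%.

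The median interval is thus about 2.6 times as wide. It includes 0 in about 70% of trials that are significant at 0.0125. It is imprecise but valid.

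**3. The other planned estimate.** Using the no-tie null variance, the SE of P(90°C better) is about √[237/(12 × 118 × 118)] = 0.038. Around 0.648 the 95% interval is roughly 0.648 ± 0.074, or 0.57 to 0.72. At 98.75% it is 0.648 ± 0.094, or 0.55 to 0.74. Both exclude 0.50. A significant result therefore has a planned estimate that agrees with it.

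**4. Dependence on the no-relief share.** The last two rows below use the four-category distribution, with responders always split 9:37:16 and uniform within category. For a no-relief share p, the median is 0 if p ≥ 0.5. Otherwise it is 25 + 50 × [0.5 − p − (9/62)(1 − p)] / [(37/62)(1 − p)] when it lies between 25 and 75, and 25 × (0.5 − p)/[(9/62)(1 − p)] when it lies below 25. The mean among responders is (0.09 × 12.5 + 0.37 × 50 + 0.16 × 87.5)/0.62 = 33.625/0.62 = 54.2. Cells give median difference / mean difference by 80°C no-relief share.

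| How the benefit arises | 38% | 50% | 60% |
|---|---|---|---|
| Every patient +15, capped at 100 (the planning effect) | 15.0 / 14.3 | 15.0 / 14.4 | 15.0 / 14.5 |
| Pattern of the plan's table | 16.5 / 13.9 | 19.6 / 14.0 | 18.1 / 14.3 |
| Responders only +15 | 15.0 / 8.6 | 0 / 6.9 | 0 / 5.5 |
| 15 percentage points fewer with no relief | 13.2 / 8.1 | 32.2 / 8.1 | 15.7 / 8.1 |
| No-relief share halved | 15.8 / 10.3 | 40.8 / 13.6 | 36.8 / 16.3 |

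The first row is the effect the plan states, and there the median difference does not move. The mean is constant in the fourth row only because that row fixes the benefit at 0.15 × 54.2 = 8.1. With the share halved it is 54.2 × p/2 and rises with p; with a gain for responders only it falls.

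**5. Shares in the documents.** The only no-relief percentages given are 38% (80°C) and 19% (90°C). None is given by visit.

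**6. A Hodges-Lehmann shift as a substitute.** Take the fourth row at a 50% share, so 35% at 90°C. P(90°C strictly better) = 0.65 × 0.50 + ½ × 0.50 × 0.65 = 0.4875, and P(strictly worse) = 0.50 × 0.35 + ½ × 0.50 × 0.65 = 0.3375. Both are below one half, so the Hodges-Lehmann shift is exactly 0, where the median difference is still 32.2.

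**The case for a change.** The strongest case is that the median difference is the only primary effect size in points, the scale on which the trial was sized, and that its margin of about 22 exceeds the 15-point target. Stopping at an efficacy boundary widens it further: under a uniform shift the 95% half-width averages 28.7, against 11.1 for the mean. If the benefit did come through fewer non-responders, as the retrospective 38% versus 19% partly suggests, and if the no-relief share passed one half, the median difference could jump or fall to 0. The bootstrap interval would also lose coverage: with 15 points fewer non-responders, from 94% at a 38% share to 87% at 60%. An added mean costs one sentence.

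The width stands, and so does the arithmetic under those conditions. The conditions lack support. The plan does say "Need for repeated RFA procedure over one year period will be analyzed as a count variable", but it gives no repeat rate and provides for more than one repeat being very rare; this is no evidence of rising no-relief shares. The opioid comparison does not carry over either. With over 60% of patients at zero the median itself would be zero, whereas at 38% it is not. A mean is a different quantity rather than a corrected median, and for pain scores the plan already tests mean reduction, through the mixed model for VAS under Secondary hypotheses.

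The missing confidence level is a true observation. The primary decision is taken from P-values, however, so it changes no result.

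**Conclusion.** The concern does not hold. The planned summary is legitimate: the median interval is wide (about ±22 points, against ±8 for a mean) but covers at about its nominal rate at the plan's 38% no-relief share, and the estimate that matches the Wilcoxon test is reported beside it with its own interval. The test, type I error and N = 216 or 237 are untouched. A significant P-value beside a median interval that includes 0 is no contradiction, since the two address different quantities.

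Instability between visits appears only if the benefit is not a uniform shift and the no-relief share lies well above anything documented; in those settings the mean may move too. Preferring a mean for a bounded outcome with many zeros is a matter of taste, and naming the confidence level is a matter of reporting detail.

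This rests on values uniform within the plan's categories, complete data, 118 patients per arm, a 95% level that the plan does not itself state, and no-relief shares above 38% taken purely as a range.
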